#### 4.4.6 Baseline Zika status

The Zika serostatus at baseline is defined as the presence of Abs against Zika in the baseline blood sample (by Zika 50% microneutralization). The baseline Zika status will be derived for each subject as follows:

- Zika immune subjects (seropositive) at baseline are defined as those subjects with titers  $\geq 100$  (1/DIL) with the parental Zika virus .
- Zika non-immune subjects (seronegative) at baseline are defined as those subjects with titers  $< 100$  (1/DIL) (not quantified) for parental Zika virus with available and “valid” results (i.e. not coded “NR”) in the serology database
- Otherwise the baseline status will be classified as undetermined and subjects will have their Zika baseline status derived as non-immune.

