7.4 Future Use of Stored Serum Samples for Research

Any unused part of the serum samples will be securely stored at the Sanofi Pasteur serology laboratory (GCI) for at least 5 years after the last license approval in the relevant market areas has been obtained for the vaccine being tested.

Subjects or subjects' parents/legally representatives will be asked to indicate in the ICF whether they will permit the future use of any unused stored serum samples for other tests. If they refuse permission, the samples will not be used for any testing other than that directly related to this study. If they agree to this use, they will not be paid for giving permission (anonymity of samples will be ensured). The aim of any possible future research is unknown today, and may not be related to this particular study. It may be to improve the knowledge of vaccines or infectious diseases, or to improve laboratory methods. Genetic tests will never be performed on these samples without individual informed consent.

8 Clinical Supplies

Sanofi Pasteur will supply the trial sites with protocols, ICFs, AF, CRFs, DCs, memory aids, and other trial documents, as well as with the following trial materials: all study vaccines and injection materials, blood collection tubes, cryotubes, cryotube storage boxes, cryotube labels, temperature recorders, shipping containers, rulers, and digital thermometers.

The means for performing Electronic Data Capture (EDC) will be defined by Sanofi Pasteur. If a computer is provided by Sanofi Pasteur, it will be retrieved at the end of the trial.

The Investigator will supply all vaccination supplies, phlebotomy, and centrifugation equipment, including biohazard and/or safety supplies. The biohazard and safety supplies include needles and syringes, examination gloves, laboratory coats, sharps disposal containers, and absorbent

countertop paper. The site will ensure that all biohazard wastes are autoclaved and disposed of in accordance with local practices. The Investigator will also supply appropriate space in a temperature-monitored refrigerator for the storage of the products and for the blood samples, and appropriate space in a temperature-monitored freezer for serum aliquots.

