#### 4.4.7 Baseline flavivirus (FV) status

##### Flavivirus (FV) status at baseline is defined as

- Immune for subjects with quantified ( $\geq 10$  (1/DIL)) neutralizing Abs against at least one dengue serotype and  $\geq 100$  (1/DIL) against Zika virus in the baseline sample.
- Non-immune for subjects without quantified ( $< 10$  (1/DIL)) neutralizing Abs against any of the four dengue serotypes and  $< 100$  (1/DIL) against Zika virus in the baseline sample. To be classified in this group, all of the titers planned to be measured at baseline must be available, and “valid” results (i.e., not coded “NR”) in the serology database
- Otherwise the baseline status will be classified as undetermined and subjects will have their FV baseline status derived as non-immune.

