## 5.2.5 Populations Used in Analyses

The main immunogenicity analyses (non-inferiority tests) will be performed on the per protocol analyses sets PPX and PPC respectively for Cervarix and CYD dengue vaccine comparisons. The subjects will be analyzed by the vaccine group to which they were randomized.

All other immunogenicity analyses will be performed on the FAS and by baseline dengue status. Subjects will be analyzed by the vaccine group to which they were randomized.

The safety analyses will be performed on the SafAS. Subjects will be analyzed according to the vaccine they actually received and by baseline dengue status.

Complementary analyses on Zika and FV baseline statuses (and by baseline dengue status) will be performed on randomized subjects and on the FAS.

Dengue GMTs by Zika and by FV baseline statuses by Zika baseline status will be performed on all subjects and on FAS dengue immune subjects.

Description of immune response to each dengue serotype according to Zika status at baseline will be performed on FAS dengue immune subjects.

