## 5.7 Changes in the Conduct of the Trial or Planned Analyses

According to Protocol amendment 1, the study population for the non-inferiority is reduced to the dengue immune subjects (seropositive) compared to initial sample size.

The full analysis set for dengue immune (seropositive) subjects population described in the protocol is no more useful because results for immunogenicity and safety will be presented by baseline dengue status.

To further assess the potential impact of prior infection by zika on the immune response induced by the CYD dengue vaccine and on dengue injection, an exploratory analysis will be performed on subjects who have accepted further testing on their BS in the ICF. Description will be done according to Zika and FV baseline status and on dengue characteristic according to the Zika and FV baseline status.

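### The SAP does not settle whether girls never tested for Zika enter the exploratory Zika and flavivirus tables, and its default rule would count them as non-immune

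*SAP*

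**What the plan says.** - **Who is tested.** SAP 5.7 states that "an exploratory analysis will be performed on subjects who have accepted further testing on their BS in the ICF". This matches the consent question in Protocol 7.4: "If they refuse permission, the samples will not be used for any testing other than that directly related to this study". No Zika assay appears among the assessment methods in Protocol Section 9, so a girl who refuses should have no Zika titre.
- **How status is derived.** SAP 4.4.6 sets the immune cut-off at a titre of 100 (1/dil). Its non-immune definition requires an available, valid titre below 100. The last bullet then covers everyone else: the status is classed as undetermined, and such "subjects will have their Zika baseline status derived as non-immune".
- **Flavivirus status.** SAP 4.4.7 closes with the same clause: "Otherwise the baseline status will be classified as undetermined and subjects will have their FV baseline status derived as non-immune".
- **Which subjects enter the tables.** SAP 5.2.5: "Complementary analyses on Zika and FV baseline statuses (and by baseline dengue status) will be performed on randomized subjects and on the FAS". It places dengue GMTs by Zika and FV status on all subjects and on dengue-immune FAS subjects, and the dengue response by Zika status on dengue-immune FAS subjects. The definitions of the FAS (5.2.1) and of randomized subjects (5.2.4) do not require a Zika result, and SAP 5.2 defines no Zika-tested set.
- **Missing data.** SAP 5.3.2 rules out imputing missing immunogenicity data.
- **Standing of the tables.** SAP 5.1.3 describes them as exploratory and descriptive, for Appendix 15.

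**The concern.** The SAP sections do not clearly fit together. One makes Zika testing depend on permission. Another names table populations that include girls who may have refused. A third assigns any girl without a usable result to the non-immune group. A programmer working from 4.4.6 and 5.2.5 alone would treat an assay that was never run as a negative result, which also sits badly with the no-imputation rule in 5.3.2.

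SAP 5.7 gives the purpose as assessing whether prior Zika infection affects the response to the dengue vaccine. That needs a reference group known to be Zika-negative. If the group includes untested girls, some may be truly immune. The prevalence table then understates Zika exposure, and the GMT comparison is between tested-positive girls and a mixture.

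The FV rule has a sharper consequence. FV-immune status requires both a positive dengue titre and a positive Zika titre. A girl with measured dengue antibody but no Zika result meets neither FV definition, so she is labelled FV non-immune despite that antibody.

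**Working it through.** The plan states no acceptance rate, Zika prevalence or tested number, so it has no figure of its own to reproduce here. The check has two steps: what each reading of the text does, and how large the effect is under assumed values.

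**Step 1. Two readings**

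| Reading | Refusers in the tables? | Who is miscoded |
|---|---|---|
| 5.2.5 taken as written | Yes | Refusers, plus consenters with a missing or non-reportable result |
| 5.7 taken to limit the 5.2.5 populations | No | Only consenters with a missing or non-reportable result |

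**Step 2. Size under the first reading**

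Inputs:
- N = 480 planned subjects (SAP 5.5).
- c = share of girls with a valid Zika result: assumed, 0.50 to 0.95.
- q = true Zika seroprevalence: assumed, 0.30 and 0.50.
- Being tested is assumed unrelated to Zika status and to dengue titre.
- For tables restricted to dengue-immune girls, c and q are the values within that subgroup.

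Formulas:
- Apparent prevalence = c × q
- Truly immune share of the derived non-immune group = (1 − c)q / (1 − cq)
- Share of the true log10 GMT difference retained = (1 − q) / (1 − cq)
- A true GMT ratio of 2 appears as 2 raised to the retained share

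Example with c = 0.70 and q = 0.30:
- apparent prevalence 0.70 × 0.30 = 0.21;
- truly immune share (0.30 × 0.30) / (1 − 0.21) = 0.09 / 0.79 = 0.114;
- retained 0.70 / 0.79 = 0.886;
- a ratio of 2 appears as 1.85.

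| c | Untested of 480 | q | Apparent prevalence | Truly immune in 'non-immune' | Contrast retained | Ratio of 2 appears as |
|---|---|---|---|---|---|---|
| 0.95 | 24 | 0.30 | 28.5% | 2% | 98% | 1.97 |
| 0.95 | 24 | 0.50 | 47.5% | 5% | 95% | 1.94 |
| 0.80 | 96 | 0.30 | 24% | 8% | 92% | 1.89 |
| 0.80 | 96 | 0.50 | 40% | 17% | 83% | 1.78 |
| 0.70 | 144 | 0.30 | 21% | 11% | 89% | 1.85 |
| 0.70 | 144 | 0.50 | 35% | 23% | 77% | 1.70 |
| 0.50 | 240 | 0.30 | 15% | 18% | 82% | 1.77 |
| 0.50 | 240 | 0.50 | 25% | 33% | 67% | 1.59 |

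A simulation of 2,000,000 subjects (c = 0.7, q = 0.5, true log10 difference 0.301, SD 0.7) agreed. Apparent prevalence was 0.350, and the difference was 0.232, against 0.302 in tested girls only. At c = 1 there is no bias.

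Without the independence assumption, apparent prevalence is the share of all girls who are both tested and positive. It need not equal c × q, but it cannot exceed the true prevalence over all girls. The GMT contrast has no such bound and could move either way.

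**The case against.** The strongest reply is that SAP 5.7 already supplies the limit. It says on whom the exploratory analysis is run, and 5.2.5 can be taken as naming the base sets within which consenting girls are selected. Refusers would then never enter the tables. This reading is fair and the documents do not exclude it. A reader might infer that the two sections flatly contradict each other, or that dilution is certain; the text supports only an ambiguity that has to be resolved. The ambiguity is real, because 4.4.6 derives a status for each subject and no Zika-tested set is defined.

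Three other stronger inferences are tempting:

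- **That untested girls are a large share of the trial.** Nothing in the documents says so. No acceptance rate is given, and the effect is small if nearly all accepted.
- **That the GMT contrast is always pulled toward no difference.** This needs testing to be unrelated to Zika status and dengue titre. If acceptance varied with either, for example by site, the direction would be unknown.
- **That the dengue rule differs because it catches only a few invalid results.** SAP 4.4.5 has the same default. The Visit 1 footnote in Protocol 5.1.4 lets a girl be vaccinated when no blood could be obtained, so wholly missing results fall under that rule too. What stands is narrower: baseline dengue serostatus was to be determined for all participants, while Zika testing depends on permission.

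The reply that the tables carry little weight also stands. No hypothesis, power figure or per-protocol exclusion uses Zika status.

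**Conclusion.** The point holds as a defect in SAP wording with limited reach. Read literally, 4.4.6, 4.4.7 and 5.2.5 count girls without a Zika result as Zika or FV non-immune. If testing is unrelated to Zika status, the relative understatement of Zika prevalence equals the untested share. If testing is also unrelated to dengue titre, between 67% and 98% of the log10 GMT contrast remains over the assumed ranges. These figures show sensitivity and do not estimate what happened in the trial. If 5.7 governs, only missing or non-reportable results among consenters are miscoded.

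A reader might infer that the non-inferiority conclusions are at risk. They are not: PPX and PPC exclude on baseline dengue status, and Zika status appears only in the exploratory Appendix 15 output.

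**What to change.** - **SAP 5.2.5:** restrict every table by Zika or FV status to girls who agreed to further testing and have a valid baseline Zika titre, in line with 5.7.
- **SAP 4.4.6 and 4.4.7:** delete the step that turns undetermined into non-immune. Show 'not tested / undetermined' as a separate count outside the denominators. Changing 4.4.6 alone would leave the same miscoding in the FV tables.
- **Reporting:** give the number tested in each group, so that readers can see how far the tested girls represent the trial.

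This needs only changes to SAP wording and table shells. The cost is smaller denominators in exploratory tables, about 480 × c: for example 456 at 95% tested, 336 at 70% or 240 at 50%. With testing unrelated to Zika status and dengue titre, the prevalence and the contrast then carry no dilution at any value of c. If testing is related to either, the restricted tables describe the tested girls only, which the reported numbers would make plain.

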#### 4.4.7 Baseline flavivirus (FV) status

##### Flavivirus (FV) status at baseline is defined as

- Immune for subjects with quantified ( $\geq 10$  (1/DIL)) neutralizing Abs against at least one dengue serotype and  $\geq 100$  (1/DIL) against Zika virus in the baseline sample.
- Non-immune for subjects without quantified ( $< 10$  (1/DIL)) neutralizing Abs against any of the four dengue serotypes and  $< 100$  (1/DIL) against Zika virus in the baseline sample. To be classified in this group, all of the titers planned to be measured at baseline must be available, and “valid” results (i.e., not coded “NR”) in the serology database
- Otherwise the baseline status will be classified as undetermined and subjects will have their FV baseline status derived as non-immune.

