#### 4.4.5 Baseline Dengue status

The dengue serostatus at baseline is defined as the presence of Abs against at least one dengue serotype in the baseline sample (by dengue 50% plaque reduction neutralization test [PRNT50]) in the blood sample collected at V01 for group 1 and at V02 for group 2. The baseline dengue status will be derived for each subject as follows:

- Dengue immune subjects (seropositive) at baseline are defined as those subjects with titers  $\geq 10$  (1/DIL) for at least one serotype with the parental dengue virus strain.
- Dengue non-immune subjects (seronegative) at baseline are defined as those subjects with titers  $< 10$  (1/DIL) (not quantified) for all serotypes with parental dengue virus strains with available and “valid” results (i.e. not coded “NR”) in the serology database.
- Otherwise the baseline status will be classified as undetermined and subjects will have their dengue baseline status derived as non-immune.

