### 5.1.3 Complementary output

Additional exploratory descriptive analyses based on baseline Zika and FV statuses will be provided in Appendix 15.

- Zika and FV baseline status
- Zika and FV baseline status by baseline dengue status
- Dengue GMTs by Zika and FV baseline status
- Description of immune response to each dengue serotype according to Zika status at baseline

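### SAP 4.4.7 labels subjects with antibody to only one of dengue and Zika as flavivirus non-immune, which mislabels the exploratory FV tables

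*SAP*

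**What the plan says.** SAP 4.4.7 sets three rules for baseline FV status.

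- Immune: quantified (titre ≥10) "neutralizing Abs against at least one dengue serotype and" a titre of at least 100 "against Zika virus in the baseline sample".
- Non-immune: below 10 for all four dengue serotypes and below 100 for Zika, with every planned baseline titre available and valid.
- Everyone else: "Otherwise the baseline status will be classified as undetermined and subjects will have their FV baseline status derived as non-immune".

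The two neighbouring definitions work differently. In SAP 4.4.5, "Dengue immune subjects (seropositive) at baseline are defined as those subjects with titers" of at least 10 for one or more serotypes. In SAP 4.4.6, a Zika titre of at least 100 means Zika immune. In both, the fallback can only catch missing or non-reportable (NR) results.

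FV status is used in three places.

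- SAP 5.1.3: "Additional exploratory descriptive analyses based on baseline Zika and FV statuses will be provided in Appendix 15".
- SAP 5.2.5: "Complementary analyses on Zika and FV baseline statuses (and by baseline dengue status) will be performed on randomized subjects and on the FAS", and "Dengue GMTs by Zika and by FV baseline statuses by Zika baseline status will be performed on all subjects and on FAS dengue immune subjects".
- SAP 5.7, which gives the purpose as assessing prior Zika infection and says that "an exploratory analysis will be performed on subjects who have accepted further testing on their BS in the ICF".

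**The concern.** A subject with complete, valid results and antibody to exactly one virus meets neither the immune nor the non-immune rule. She falls to the fallback, is called undetermined although nothing is missing, and is printed as non-immune. The label then covers people who fail the SAP's own non-immune rule precisely because they are positive.

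It also conflicts with the protocol's usage. Protocol 1.1 places dengue virus in the Flavivirus genus, and Protocol 6.1.1.3 contrasts FV-naive with FV-immune populations. In that usage a dengue-immune subject cannot be FV non-immune.

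At stake is the reading of the Appendix 15 tables. In the all-subjects table of dengue GMTs by FV status, the non-immune row would pool truly negative subjects with dengue-immune ones. A reader would take it as the response in flavivirus-naive girls, which it is not.

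**Working it through.** The documents state no figure for FV status, so there is none to reproduce. The check is a full enumeration of the rules.

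Notation: dengue D+ (any serotype ≥10), D− (all four valid and <10), Dm (no positive titre and at least one missing/NR); Zika Z+ (≥100), Z− (valid and <100), Zm (missing/NR). The right-hand column replaces *and* with *or* in the immune rule and leaves the rest unchanged.

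| Pattern | SAP 4.4.7 as written | With *or* |
|---|---|---|
| D+ Z+ | immune | immune |
| D+ Z− | fallback → non-immune | immune |
| D+ Zm | fallback → non-immune | immune |
| D− Z+ | fallback → non-immune | immune |
| Dm Z+ | fallback → non-immune | immune |
| D− Z− | non-immune | non-immune |
| D− Zm | fallback → non-immune | fallback |
| Dm Z− | fallback → non-immune | fallback |
| Dm Zm | fallback → non-immune | fallback |

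1. Patterns with a positive titre: the first five rows. As written, 4 of 5 become FV non-immune. With complete data there are four patterns (D+Z+, D+Z−, D−Z+, D−Z−), and the two single-positive ones are mislabelled.
2. Reach of the fallback: 7 of 9 patterns as written, 3 of 9 with *or*. Those three have no positive titre and at least one missing/NR result, which is all that the fallback catches in SAP 4.4.5 and 4.4.6.
3. Within dengue-immune subjects (D+Z+, D+Z−, D+Zm): as written, FV immune if and only if Z+. SAP 4.4.6 also derives Zm as Zika non-immune, so FV status equals derived Zika status in 3 of 3 patterns. The FV table in FAS dengue-immune subjects repeats the Zika table under another name. With *or*, FV status is immune in all three, hence constant.
4. Untested subjects: SAP 5.7 restricts the exploratory work to those who accepted further testing, whereas SAP 5.2.5 names randomized subjects and the FAS without that restriction. If the tables are run on the populations in 5.2.5, a dengue-immune subject never tested for Zika (D+Zm) prints as FV non-immune.
5. Reach beyond Appendix 15: PPX and PPC (SAP 5.2.2) exclude on dengue status, and the other immunogenicity analyses and the safety analyses (SAP 5.2.5) are split by dengue status. None uses FV status.

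Illustration only, since the documents give no prevalences. Let d and z be the dengue and Zika seropositive proportions among subjects with both results, assumed independent. Single-positive share = d(1−z) + z(1−d); double-negative share = (1−d)(1−z).

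- d = 0.3, z = 0.1: single-positive 0.27 + 0.07 = 0.34; double-negative 0.63; single-positives are 0.34/0.97 = 35% of the FV non-immune group.
- d = 0.8, z = 0.1: single-positive 0.72 + 0.02 = 0.74; double-negative 0.18; 0.74/0.92 = 80%.
- d = 0.8, z = 0.5: single-positive 0.40 + 0.10 = 0.50; double-negative 0.10; 0.50/0.60 = 83%.

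Over assumed ranges d = 0.3–0.8 and z = 0.1–0.5, single-positives are 34–74% of subjects with both results and 35–83% of the FV non-immune group. Without independence the range widens: if d = z and the two statuses agreed in every subject, there would be no single-positives.

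**The case against.** The strongest reply has four parts.

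First, the output is exploratory, and its stated purpose, the effect of prior Zika infection, is served by Zika status, which SAP 4.4.6 defines soundly. That is right and limits the importance of the point.

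Second, the planned table of Zika status by dengue status lets a reader recover how many single-positives there are, on derived statuses. That holds for counts. It does not repair a GMT computed on a mixed row.

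Third, the SAP never says what FV status is meant to represent, and it plans dengue GMTs by FV status within dengue-immune subjects. That split has two levels under *and* but only one under *or*, so immunity to both viruses may have been intended. This is a fair reason to ask the sponsor, but it does not rescue the labels: under that reading a single-virus positive is still not non-immune. Nor does redundancy with Zika status decide between the readings. Under *or*, FV status matches derived Zika status among dengue non-immune subjects instead.

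Fourth, the pattern counts are not subject counts, and SAP 5.7 may be meant to limit the tables to consenting subjects. Both stand. The point about untested subjects is conditional on how 5.2.5 is applied, and showing undetermined subjects separately is a preference.

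**Conclusion.** The concern holds. Followed exactly, SAP 4.4.7 gives the wrong label in four of the five result patterns that contain a positive titre, and it makes the all-subjects FV non-immune GMT row a mixture of flavivirus-negative and dengue-immune subjects. This follows from the text alone and needs no assumption about prevalence. It takes immune in its ordinary sense, as the SAP's own non-immune rule, its dengue and Zika definitions, and the protocol's usage all support.

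How many subjects are affected is unknown; the percentages above are illustrations under assumed prevalences. The consequence is limited to three exploratory outputs: FV status, FV status by dengue status, and dengue GMTs by FV status. No confirmatory conclusion, analysis set, power figure or safety analysis changes. It should be corrected, but it does not threaten the trial's main results.

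**What to change.** In SAP 4.4.7, define FV immune as a dengue titre ≥10 for at least one serotype *or* a Zika titre ≥100. Keep the non-immune rule as it stands, so that the fallback covers only subjects with no positive titre and a missing/NR result. In SAP 5.2.5, drop dengue GMTs by FV status within FAS dengue-immune subjects and keep the Zika split there.

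If the sponsor meant immunity to both viruses, rename the category accordingly and show single-virus positives in their own row.

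Optionally, show undetermined subjects, including those not tested for Zika, as a separate row, and state in 5.2.5 whether the consent restriction in 5.7 applies. A separate row would depart from the SAP's convention of recoding undetermined to non-immune for all three statuses.

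The cost of the main change is one word in 4.4.7, one sentence in 5.2.5 and the reprogramming of one derived variable. One table split is lost, and the Zika table already supplies that contrast.
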